#### **4.2.4 Supplementary Analyses**

Not applicable.

### **4.3 Secondary Endpoints Analysis**

#### **4.3.1 Key Secondary Endpoints**

The components of the primary endpoint, ABR (total, joint, spontaneous) and frequency of administration (infusions/month), will be presented via summary statistics. Values for the study period and intra-individual change from pre-study value will be presented for total ABR and frequency of administration. In addition, the proportion and 95% exact (Clopper-Pearson) CIs of participants with improved/similar/worse value of total ABR and frequency of administration will be provided. These tables will be presented overall.

Frequency tables will be provided for the proportion of participants with 0,  $>0$  and  $\leq 1$ , and  $>1$  spontaneous bleeds. Corresponding 95% CIs will be reported for the proportions with 0 or with 0 to  $\leq 1$  spontaneous bleeds.

##### **4.3.1.1 Definition of Endpoints**

Refer to [section 4.1](#) and [section 4.2.1](#).

#### 4.3.1.2 Main Analytical Approach

Refer to [section 0](#).

#### 4.3.1.3 Sensitivity Analysis

In addition to the analysis of treated bleeds ABR, all bleed ABR will be presented via summary statistics for all bleed ABR, the annualized rate of all bleeds (regardless of treated or untreated) and the intra-individual difference between all bleed and treated bleed ABR.

### 4.3.2 Supportive Secondary Endpoints

The analyses of supportive secondary endpoints will be performed on the mITT population. The entire study intervention period will be analyzed regardless of the dosing regimen (i.e. entire period includes the first 8 weeks).

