### 9.4.1 General Considerations

Statistical analyses will be performed using SAS release 9.2 or higher (SAS Institute Inc., Cary, North Carolina, United States [US]). The version used will be specified in the SAP.

All variables will be analyzed descriptively with appropriate statistical methods: categorical variables by frequency tables (absolute and relative frequencies) and continuous variables by sample statistics (i.e. mean, standard deviation [SD], minimum, median, quartiles, and maximum). Continuous variables will be described by absolute value and as change from baseline per analysis time point, if applicable.

All endpoints will be analyzed according to the modified intention-to-treat (mITT). The entire study period will be analyzed regardless of the regimen.

Some tables will be stratified by the risk score-selected dosing regimen. Additionally, some selected tables (including the primary endpoint, safety events, study intervention administration, prophylaxis regimen, and PK parameters) will be presented in total and by subgroup of history of FVIII inhibitors for sensitivity purposes.

In general, missing clinical outcomes collected in this study will not be imputed. Missing exposure and AE/concomitant medication start/end date will be imputed based on a worst-case scenario.

Baseline is defined as time point of enrollment into study. The participant total risk score will be calculated at baseline and the resulting prophylaxis regimen will be assigned as describe in [Section 4.1](#).

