### **11.7.5 Visit 6 – (Month 6, End of Study/Early Withdrawal)**

This in-person visit should take place in alignment with the weekly prophylaxis regimen (i.e. as close as possible to the participant's next infusion) as follows: on Day 4 for participants on the 2x/week regimen, on Day 5 for participants on the Q5D regimen, and on Day 7 for participants on less frequent regimens (e.g. Q7D).

The following procedures and assessments will be performed in participants at the EOS visit or at the time of premature termination:

- Concomitant medication review
- AE/SAE/AESI review
- Physical examination including height and weight
- Assessment of joint status
- Collect information on physical activity level (medium/high [contact sports]; low [non-contact sports]; sedentary)
- Blood sample collection **before** administration of study intervention: FVIII (Jivi) trough levels
  - Sample collection on Day 4 for participants on the 2x/week regimen, on Day 5 for participants on the Q5D regimen, and on Day 7 for participants on less frequent regimens (e.g. Q7D)
- Pregnancy test (female participants)
- In-hospital infusion of Jivi
- If the PI feels the baseline peak FVIII level at 15-30 minutes or 4-8 hours post-infusion at Visit 2 does not seem to be appropriate for the dose infused, then the levels should be repeated at Visit 5 and the results also uploaded to WAPPS-Hemo. For those patients who do not have appropriate FVIII levels at either Visit 2 or Visit 5, the levels should be repeated at Visit 6.
- Administration and completion of PROs (Haem-A-QoL or Haemo-QoL, EQ-5D-5L, TSQM, WPAI, and Patient's Global Impression of Change [PGI-C])
- Return used and unused vials
- Check of eDiary entries and bleeding history

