**Table 3: Analysis Sets**

Participant Analysis Set	Description
Enrolled	All participants who signed the ICF
Modified intention-to-treat (mITT) set	All enrolled participants who had received at least 1 dose of study intervention, who have infusions/bleeding data from the diary and CRF available, and who have been followed for a minimum of 4 months.
Safety analysis set	All participants who had received at least 1 dose of study intervention.

Abbreviations: CRF = case report form; ICF = informed consent form.

Final decisions regarding the assignment of participants to analysis sets will be made during the review of study data and documented in the final list of important deviations, validity findings and assignment to analysis set(s).

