## 4. Statistical Analyses

### 4.1 General Considerations

Statistical analyses will be performed using SAS release 9.4 or higher (SAS Institute Inc., Cary, North Carolina, US).

All variables will be analyzed descriptively with appropriate statistical methods: categorical variables by frequency tables (absolute and relative frequencies) and metric (or continuous) variables by sample statistics (i.e. mean, standard deviation [SD], minimum, median, quartiles, and maximum). The number of data available and missing data will be calculated

for metric data. Continuous variables will be described by absolute value and as change from baseline per analysis time point, if applicable.

All data will be presented in the participant data listing as they are recorded on the electronic case report form (eCRF), eDiary and Interactive Voice/Web Response System (IxRS), i.e. partially missing data will appear as such.

The primary analysis will be performed after the database lock after Last Participant Last Visit.

The mITT set will be used to analyze endpoints related to the effectiveness objectives and the safety analysis set will be used to analyze the endpoints and assessments related to safety. Data will be pooled across study sites for all reporting of participant characteristics, primary, secondary, and safety endpoints.

Analysis will be presented overall for the combined risk score groups. Some tables will be stratified by the risk score-selected dosing regimen. Analysis of risk score-selected dosing regimen will include the entire treatment period. The first 8 weeks on study will not be presented separately. Safety listings will include assigned dosing regimen, based on risk score, and actual current dosing regimen at start of AE or time of assessment. Safety summaries will be presented only overall, for the combined risk score groups.

Subgroup analysis of study endpoints and safety events by history of FVIII inhibitors will be presented only if the mITT set includes at least 5 participants in each category, with and without history of FVIII inhibitors.

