### 4.2.2 Main Analytical Approach

The analysis of the primary endpoint will be performed on the mITT population.

The entire study intervention period will be analyzed regardless of the score assigned dosing regimen (i.e. during the first 8 weeks on the study).

The strategy for primary endpoint analysis, including how to deal with participants who switch regimen frequency is listed below:

- A switch to a higher frequency regimen than the one assigned by the score, due to a bleed during study, is considered as non-favorable outcome
- Participants who switch due to other reasons than bleeding events (e.g. personal decision, study compliance issues, or changes in physical activity level) will be censored at the time of regimen change
  - switch after 4 months ( $> 122$  days): participant data will be analyzed until censoring
  - switch prior to 4 months ( $\leq 122$  days): participant data will not be used for analysis, as it is assumed that a shorter duration will not be sufficient to correctly estimate the ABR and would bias the results.

Note: a decrease in regimen per score assignment (during the first 8 weeks) is not considered a switch as discussed above.

Favorable outcome assessed by total ABR and frequency of administration (/month) is evaluated after considering regimen switch events.

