  - Scores will be presented as a frequency table and median response where 3 = very much improved, 0 = no change, and -3 = very much worse. The proportion and 95% CI of participants with any improved score at EOS will be presented.
- EuroQoL 5 Dimensions (EQ-5D-5L) questionnaire
  - Scores in 5 dimensions (Mobility, Self-Care, Usual Activities, Pain/Discomfort, and Anxiety/Depression) each will be presented as a frequency table and median response at baseline, 3 months, and EOS, where 1 = least impaired and 5 = most impaired. Since EQ-5D-5L is a descriptive system based on five independent dimensions, a missing answer or ambiguous answer (i.e. marking of more than one level on scale) will lead to complete rejection of the questionnaire, but the visual analog scale (VAS) score will be retained if available.
  - Overall health assessment VAS will be summarized at baseline, 3 months, and EOS. Intra-individual overall health assessment change from baseline at 3 months and EOS will be summarized.
- Work Productivity and Activity Impairment (WPAI) questionnaire scores for hemophilia effect over the last 7 days on productivity or ability at work, at school, and in regular daily activitiesiii
  - WPAI employment (Q1 = Yes)
    - Percent work time missed due to problems associated with your hemophilia:  $100 \times Q2 / (Q2 + Q4)$   
where Q2 = hours missed due to problems associated with your hemophilia and Q4 = hours actually worked.
    - Percent impairment while working due to health:  $10 \times Q5$   
where Q5 = how much did your hemophilia affect your productivity while you were working (scale is 0 to 10).
  - WPAI academic (Q5 = Yes)
    - Percent class time missed due to health:  $100 \times Q7 / Q8$   
where Q7 = hours missed due to problems associated with your hemophilia and Q8 = hours actually attended.
    - Percent impairment while attending classes due to health:  $10 \times Q9$
  - WPAI regular daily activities
    - Percent impairment of daily activities due to health:  $10 \times Q10$   
where Q10 = how much your hemophilia affected your ability to do

your regular daily activities, other than work at a job or attending classes (scale is 0 to 10)

- WPAI average impairment score is the mean of employment, academic and regular daily activities impairment scores

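### PROs are summarised only in the mITT set, so treated participants followed for less than 4 months enter no PRO table; an all-treated sensitivity run should be added

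*SAP*

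**What the plan says.** **Analysis set.** SAP 4.3.2, which governs the PROs and joint status, says: "The analyses of supportive secondary endpoints will be performed on the mITT population". SAP 4.1 gives the same general rule: "The mITT set will be used to analyze endpoints related to the effectiveness objectives". Protocol 9.4.1 assigns every endpoint to the mITT, so the two documents agree.

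**Who is in it.** SAP Table 3 limits the mITT to treated participants with infusion and bleeding data "who have been followed for a minimum of 4 months".

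**Why 4 months.** The only reason found in the SAP is in 4.2.2. It excludes from the primary analysis participants who switch regimen for non-bleeding reasons by day 122, because "it is assumed that a shorter duration will not be sufficient to correctly estimate the ABR and would bias the results".

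**What is collected from early leavers.** Protocol 11.7.5 schedules Haem-A-QoL or Haemo-QoL, EQ-5D-5L, TSQM, WPAI and PGI-C "at the EOS visit or at the time of premature termination". Protocol 7.1 calls for an EOS visit when study treatment is stopped for good. EQ-5D-5L is also taken at Month 3.

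**How PROs are reported.** For PGI-C, SAP 4.3.2.1 says: "The proportion and 95% CI of participants with any improved score at EOS will be presented". Missing PRO data are not imputed. The safety-set sensitivity analysis in SAP 4.2.3 concerns favorable outcome only, and runs only if more than 3 participants in the safety set are outside the mITT.

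**The concern.** Four months of follow-up is a sensible requirement for an annualized rate, because a short period gives an unstable ABR. It is not obviously needed to read a questionnaire. EQ-5D-5L asks about today, WPAI about the past 7 days, TSQM about the last two to three weeks or since last use, and Haem-A-QoL mostly about the past 4 weeks. PGI-C asks about change since the study began. The SAP gives no PRO-specific reason for the limit.

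The SAP treats exclusion from the mITT as a possible problem for the primary endpoint, since it plans a safety-set analysis there, but it has no counterpart for the PROs. Someone who stops because of an adverse event, lack of effect or dissatisfaction could complete PGI-C and TSQM on leaving and still not be counted. In a single-arm study no comparator would reveal that kind of selection in the satisfaction and improvement tables.

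**Working it through.** **Step 1: reproduce a figure from the plan.** The documents give no figure for PRO loss, so the check starts from the precision table. For 14/20 = 70%, the exact Clopper-Pearson 95% interval is 45.7% to 88.1%, width 42.4 points. This matches SAP Table 4, and every other distinct row reproduces to 0.1 point.

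**Step 2: inputs.**
- N treated: 20 or 25 (SAP section 5).
- k followed for less than 4 months: not stated, so assumed to be 1 to 5. The superseded plan of 70 enrolled for about 60 evaluable (Amendment 3 rationale) implies 10/70 = 14.3%, or 2.9 of 20 and 3.6 of 25. That is loss over the whole study, so it is only a rough guide.
- x/m, PGI-C improvement in the mITT with m = N − k: assumed to be about 70%.
- f, the share of early leavers reporting improvement: unknown, varied from 0 to 1.
- Every early leaver is assumed to have completed a PGI-C.
- Intervals are Clopper-Pearson by assumption; the SAP does not name a method for PGI-C.

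**Step 3: formula.** The mITT proportion is x/m and the all-treated proportion is (x + f·k)/N. The difference is

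x/m − (x + f·k)/N = (k/N) × (x/m − f).

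The sign depends only on whether leavers improve less or more often than stayers. The size scales with the fraction leaving.

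**Step 4: results.**

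| N | k | mITT (95% CI) | f | All treated (95% CI) | mITT minus all treated, points |
|---|---|---|---|---|---|
| 20 | 3 | 12/17 = 70.6% (44.0 to 89.7) | 0 | 12/20 = 60.0% (36.1 to 80.9) | +10.6 |
| 20 | 3 | same | 0.5 | 13.5/20 = 67.5% | +3.1 |
| 20 | 3 | same | 0.706 | 14.1/20 = 70.6% | 0 |
| 20 | 3 | same | 1 | 15/20 = 75.0% (50.9 to 91.3) | −4.4 |
| 25 | 4 | 15/21 = 71.4% (47.8 to 88.7) | 0 | 15/25 = 60.0% (38.7 to 78.9) | +11.4 |
| 25 | 4 | same | 0.5 | 17/25 = 68.0% | +3.4 |
| 25 | 4 | same | 1 | 19/25 = 76.0% (54.9 to 90.6) | −4.6 |

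Over k = 1 to 5 and f = 0 to 1, the difference runs from +16.7 to −8.3 points for N = 20 and from +14.0 to −6.0 points for N = 25.

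**Step 5: if some questionnaires are missing.** If only one of the three leavers has a PGI-C and it is not improved, the sensitivity figure is 12/18 = 66.7%, a difference of 70.6 − 66.7 = 3.9 points. The run can recover only what was collected, so the number with no questionnaire must be reported beside it.

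**The case against.** The case for leaving the plan alone has several good parts.

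- **Direction.** A reader might infer that the PRO results are inflated. The documents give no number, reason or rating for early leavers, and step 4 allows either sign. Only possible inflation is supportable.
- **Discarded data.** A reader might infer that the questionnaires are thrown away. SAP 4.1 puts all recorded data in participant listings, and SAP 4.6.1 tabulates discontinuation reasons for all enrolled participants. With a few leavers, each can be inspected.
- **Rationale.** The ABR sentence is written for regimen switchers. That it also underlies the mITT limit is an inference.
- **Who actually drops out of the tables.** Bleeding on an extended interval leads to a regimen change under Protocol 6.5, not to withdrawal. SAP 4.3.2 keeps switchers in, and anyone followed for 4 months stays in. It is also tempting to cite the loss-of-efficacy reports, but Protocol 8.4.7 describes those in children under 6 and this trial enrols from age 12.
- **Availability.** Protocol 7.2 makes the early withdrawal visit conditional on being possible, and those lost to follow-up will have no questionnaire. Protocol section 7 also encourages follow-up after leaving treatment, whereas 7.1 says such participants do not remain in the study. Those passages need reconciling, because they affect who counts as followed.
- **Meaning of early values.** Everyone starts on the same regimen for 4 weeks and low-risk participants reach their assigned one at Week 9. A questionnaire before then does not rate the score-assigned regimen, and a 4-week recall may reach back into previous treatment.
- **Importance.** The SAP follows the protocol, the analyses are descriptive, and a worst-case shift of about 10 points for 3 or 4 leavers sits inside intervals more than 40 points wide.

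All of this narrows the point, and the last two items are good reasons to keep the mITT as the main PRO set. None of it supplies a PRO table that includes the early leavers. A listing does not give a proportion, and the interval width describes sampling error, not selection.

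**Conclusion.** The point holds as a gap in the PRO analysis. Treated participants followed for less than 4 months enter no PRO summary, although their questionnaires are scheduled, and neither document gives a PRO-specific reason.

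The documents do not support a claim that the results are inflated. They support only that inflation is possible if early leavers rate treatment worse than those who stay. With 3 of 20 leaving and 70.6% improved in the mITT, the mITT figure is 10.6 points too high if none of them improved, unchanged if they improved equally often, and 4.4 points too low if all did. These figures rest on an assumed number of leavers, an assumed improvement rate and complete early-withdrawal questionnaires. What is affected is the reading of descriptive PRO tables; no test and no part of the primary analysis changes. The addition is worth making because it is cheap and uses data already planned. If nobody leaves before 4 months and no one is excluded from the mITT for another reason, both sets of tables will agree.

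**What to change.** Keep the mITT PRO tables and make these additions:

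1. In SAP 4.3.2, add a sensitivity run of the PRO summaries in all treated participants (safety analysis set) with at least one post-baseline questionnaire, using the early-withdrawal questionnaire where one exists.
2. Report the number and timing of early-withdrawal questionnaires, and the number of treated participants with none.
3. Footnote that early-withdrawal values reflect shorter exposure, sometimes before the score-assigned regimen is reached.
4. Declare the addition to Protocol 9.4.1 in SAP 4.7, which now reports no changes, and align the matching statement in SAP section 1.

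Counting a missing PGI-C as not improved is at most an optional lower bound. It imputes an outcome, which the SAP otherwise avoids, and it pulls the estimate down.

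The cost is a short SAP revision and one more set of tables, with no new data collection. The drawback is that the added tables mix different lengths of exposure, which is why they should sit beside the mITT tables and not replace them.

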#### 4.3.2.1 Patient Reported Outcomes

PRO data will be collected in an eDiary form made available for Baseline (HAEM-A-QoL or HAEM-QoL [adult or kids], EQ-5D-5L, WPAI+CIQ:HS, TSQM-9 [baseline]), Month 3 (EQ-5D-5L only), and EOS (HAEM-A-QoL or HAEM-QoL, PGI-C, EQ-5D-5L, WPAI+CIQ:HS, TSQM-9) visits. Frequency summaries will be presented by visit and continuous variables will be described by absolute value and as change from baseline. Missing data will not be imputed.

- Haemophilia Quality of Life Questionnaire transformed scale scores (%) will be presented separately for participants ages  $\geq 17$  years and for those age 12-16.
  - *HAEM-A-QoL (adult)* has 46 questions in 10 groups
  - *HAEMO-QoL KIDS (ages below 16)* short form has 35 questions

Steps to calculate total scoreii:

- Assorting: Assign the numbers to each question response
- Recoding (HAEM-A-QoL): Numeric scores will be assigned to each item so that highest score is most impaired: 1= never, 2=seldom, 3=sometimes, 4=often, 5=all the time for negatively worded items or 1=all the time, 2=often, 3=sometimes, 4=seldom, 5= never for positively worded items.
  1. Physical Health, 5 questions, no recoding is needed
  2. Feeling, 4 questions, no recoding is needed
  3. View of yourself, 5 questions, #2 and #5 must be recoded
  4. Sports and Leisure, 5 questions, #3 must be recoded
  5. Work and School, 4 questions, #1 and #2 must be recoded
  6. Dealing with Hemophilia, 3 questions, #1, #2, #3 must be recoded
  7. Treatment, 8 questions, #8 must be recoded
  8. Future, 5 questions, #2 must be recoded
  9. Family Planning, no recoding is needed
  10. Partnership and Sexuality, 3 questions, no recoding is needed
- Recoding (HAEMO-QoL KIDS): Total Score, 35 questions, #11, #12, #17, #18, #19, #27, #28, #29, #30, #31, #32 must be recoded

- Summing up the total score for each HAEM-A-QoL sub-scale and for the HAEM-A-QoL and HAEMO-QoL KIDS total scores
- Transferring a raw score to a transformed scale score between 0 and 100. The raw score range lies between the lowest possible (number of items (n) x 1) and highest possible (number of items(n) x 5) value of the respective scale. Missing items will be omitted from the raw score and also from the n used to calculate range.
- Patient's Global Impression of Change (PGI-C);
  - Scores will be presented as a frequency table and median response where 3 = very much improved, 0 = no change, and -3 = very much worse. The proportion and 95% CI of participants with any improved score at EOS will be presented.
- EuroQoL 5 Dimensions (EQ-5D-5L) questionnaire
  - Scores in 5 dimensions (Mobility, Self-Care, Usual Activities, Pain/Discomfort, and Anxiety/Depression) each will be presented as a frequency table and median response at baseline, 3 months, and EOS, where 1 = least impaired and 5 = most impaired. Since EQ-5D-5L is a descriptive system based on five independent dimensions, a missing answer or ambiguous answer (i.e. marking of more than one level on scale) will lead to complete rejection of the questionnaire, but the visual analog scale (VAS) score will be retained if available.
  - Overall health assessment VAS will be summarized at baseline, 3 months, and EOS. Intra-individual overall health assessment change from baseline at 3 months and EOS will be summarized.
- Work Productivity and Activity Impairment (WPAI) questionnaire scores for hemophilia effect over the last 7 days on productivity or ability at work, at school, and in regular daily activitiesiii
  - WPAI employment (Q1 = Yes)
    - Percent work time missed due to problems associated with your hemophilia:  $100 \times Q2 / (Q2 + Q4)$   
where Q2 = hours missed due to problems associated with your hemophilia and Q4 = hours actually worked.
    - Percent impairment while working due to health:  $10 \times Q5$   
where Q5 = how much did your hemophilia affect your productivity while you were working (scale is 0 to 10).
  - WPAI academic (Q5 = Yes)
    - Percent class time missed due to health:  $100 \times Q7 / Q8$   
where Q7 = hours missed due to problems associated with your hemophilia and Q8 = hours actually attended.
    - Percent impairment while attending classes due to health:  $10 \times Q9$
  - WPAI regular daily activities
    - Percent impairment of daily activities due to health:  $10 \times Q10$   
where Q10 = how much your hemophilia affected your ability to do

your regular daily activities, other than work at a job or attending classes (scale is 0 to 10)

- WPAI average impairment score is the mean of employment, academic and regular daily activities impairment scores
- Percentage scores for work time, impairment while working, class time, impairment while attending classes, impairment of daily activities, and WPAI average will be presented. The actual mean scores at baseline and EOS will be presented and intra-individual change from baseline to EOS.
- Treatment Satisfaction Questionnaire for Medication (TSQM);
  - Frequency summaries will be presented of individual items together with median satisfaction scale scores. Scores range from 1=Extremely Dissatisfied to 7=Extremely Satisfied for Questions 1-3 and 9, from 1=Extremely Difficult to 7=Extremely Easy for Questions 4-5, from 1=Extremely Inconvenient to 7=Extremely Convenient for Question 6, from 1=Not at All Confident to 5=Extremely Confident for Question 7, and from 1=Not at All Certain to 5=Extremely Certain for Question 8. The sum of scores for each participant will be summarized at baseline and EOS and the intra-individual sum of scores change from baseline will be summarized at EOS.

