#### **8.2.2 Patient Reported Outcomes**

The PRO data on QoL and health status, work and school productivity, pain, and treatment satisfaction will be collected. The objective of PRO data is to collect the participant's perspectives and opinions on the impact and effectiveness of Jivi in the treatment of hemophilia. Questionnaires will be filled out by the participant in the treatment center at Baseline (Day 1; Haem-A-QoL or Haemo-QoL, PGI-C, EQ-5D-5L, TSQM, and WPAI), Month 3 (EQ-5D-5L only), and Month 6 (EOS; Haem-A-QoL or Haemo-QoL, PGI-C, EQ-5D-5L, TSQM, and WPAI). [Appendix 2](#) provides representative examples of the PROs to be used in the study.

The following PROs assessments will be obtained:

- **Haemophilia specific quality of life (Haem-A-QoL and Haemo-QoL) questionnaires:**

The questionnaire will be used to capture the full impact of Jivi and the treatment modalities on the participants' hemophilia-specific QoL during the previous 4 weeks. The Haem-A-QoL is a hemophilia-specific QoL questionnaire for adults aged 18 years and above. The questionnaire has 41-items covering 6 domains: Physical Functioning, Role Functioning, Worry, Consequences of Bleeding, Emotional Impact, and Treatment Concerns. For participants 17 years and younger, the Haemo-QoL Short Form Questionnaire for children and adolescents will be used. The Haemo-QoL

Short Form contains 35 questions covering 9 domains: Physical Health, View of Yourself, Family, Friends, Others, Sports, Dealing, and Treatment.

The respondent burden for both questionnaires is approximately 15 minutes.

- **Patient's Global Impression of Change (PGI-C)**

The self-report measure PGI-C reflects a participant's belief about the efficacy of treatment. The PGI-C consists of a 7-point scale depicting a participant's rating of overall improvement. Participants rate their change as "very much improved," "much improved," "minimally improved," "no change," "minimally worse," "much worse," or "very much worse."

The respondent burden for the questionnaire is approximately 5 minutes.

- **Five-Level European Quality of Life Five Dimension (EQ-5D-5L)**

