### 1.1 Objectives and Endpoints

Objectives	Endpoints
Primary	
To assess the effect of using a baseline risk score, based on a participant's phenotypic and biologic variables, to select the most appropriate prophylaxis regimen for reaching a favorable outcome, when switching from a SHL product to Jivi	Occurrence of favorable outcome on the score selected dosing regimen
Secondary	
To assess the effectiveness of Jivi compared to a previous SHL treatment	ABR (total, joint, spontaneous) and change in total ABR from pre-study
To assess the frequency of Jivi administration	Change in the frequency of pre-study SHL treatment to the frequency of Jivi administration (infusions/month)
To assess the proportion of participants with 0 and $\leq 1$ spontaneous bleeds	Occurrence of participants with 0 and $\leq 1$ spontaneous bleeds
To assess participant quality of life (QoL) and physical activity, as measured by Patient Reported Outcomes (PROs)	Change in Haemophilia Quality of Life Questionnaire (Haem-A-QoL or Haemo-QoL KIDS, depending on age of participant); Patient's Global Impression of Change (PGI-C); EuroQoL 5 Dimensions (EQ-5D-5L) questionnaire; Treatment Satisfaction Questionnaire for Medication (TSQM); Work Productivity and Activity Impairment (WPAI) questionnaire scores
To assess target joint status, per International Society on Thrombosis and Haemostasis (ISTH) guidelines	Number of target joints and change in target joint status from baseline

Objectives	Endpoints
Other, Pre-specified	
To assess whether blood type and body mass index (BMI) would have led to a different score allocation	Participant score considering ABO type and BMI
To describe PK parameters derived from WAPPS-Hemo and assess any association with clinical risk score	PK parameters derived from WAPPS-Hemo
To determine participant Jivi trough levels while on a specific regimen	Trough measurement of Jivi levels
To determine the percentage of participants who can maintain > 1%, > 3 %, and > 5% FVIII trough levels while on a specific prophylaxis regimen	Occurrence of trough levels above 1%, 3% and 5%, stratified by prophylaxis regimen
Abbreviations: ABR = annualized bleeding rate; EQ-5D-5L = EuroQoL 5 dimensions; FVIII = human coagulation factor VIII; SHL = standard half-life	

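### Protocol and SAP split the haemophilia QoL questionnaire at different ages, so a 17-year-old's short-form score would be tabulated with adult-form scores, and a change score could span two questionnaires

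*SAP*

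**What the plan says.** Protocol 8.2.2 sets the form by age: "The Haem-A-QoL is a hemophilia-specific QoL questionnaire for adults aged 18 years and above", and "For participants 17 years and younger, the Haemo-QoL Short Form Questionnaire for children and adolescents will be used". The short form reproduced in Protocol 11.2.1 is itself printed for ages 8 to 16.

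SAP 4.3.2.1 states: "Haemophilia Quality of Life Questionnaire transformed scale scores (%) will be presented separately for participants ages" 17 and over "years and for those age 12-16". The two forms are listed directly beneath that split. The adult form "has 46 questions in 10 groups"; the short form has 35 questions and carries the label "HAEMO-QoL KIDS (ages below 16".

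SAP 1.1 says only "Haem-A-QoL or Haemo-QoL KIDS, depending on age of participant", without a reference date. For PRO data in general, "continuous variables will be described by absolute value and as change from baseline". Change on this questionnaire is a listed secondary endpoint in Protocol 3 and SAP 1.1. SAP sections 1 and 4.7 report no departures from the protocol's analyses.

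**The concern.** The collection rule and the tabulation rule disagree for 17-year-olds. Followed as written, they place a short-form score in the stratum meant for adult-form scores. Both forms are rescaled to 0-100, so a summary table would not show the mixing.

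There is also no rule for a birthday on study. Protocol 11.1.3 provides for re-consent when a minor comes of age, but has no counterpart for the questionnaire. If the site changes the form between baseline and Month 6, the resulting difference is between two instruments and cannot be read as a change in quality of life.

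**Working it through.** **Do the forms differ?** Counting items on the Haem-A-QoL printed in Protocol 11.2.1 gives 5+4+5+5+4+3+8+5+4+3 = 46 in 10 groups, which reproduces the SAP's figure. (The text of Protocol 8.2.2 describes 41 items in 6 domains; that is a separate inconsistency and does not affect this point.) The short form has 35 items. With items scored 1 to 5:

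- adult form: raw score from 46 × 1 = 46 to 46 × 5 = 230
- short form: raw score from 35 × 1 = 35 to 35 × 5 = 175

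The SAP derives sub-scale scores for the adult form only, and a total for both. A 17-year-old on the short form would therefore contribute to the total in the older stratum and to none of its sub-scales.

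**Each age under each stated rule**

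| Age | Form under Protocol 8.2.2 | SAP stratum | SAP short-form label (below 16) | Range printed on short form (8-16) |
|---|---|---|---|---|
| 15 | Short form | 12-16 | Inside | Inside |
| 16 | Short form | 12-16 | Outside | Inside |
| 17 | Short form | 17 and over | Outside | Outside |
| 18 | Adult form | 17 and over | Outside | Outside |

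Age 17 is the only row where the protocol's form and the SAP's stratum disagree. At age 16 only the SAP's label is out of line.

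**How many participants?** The documents give no age distribution. As an assumption, take ages uniform over whole years in a range of w years, with N = 20 to 25 (Protocol 9.2):

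- expected number aged 17 = N / w; chance of at least one = 1 − (1 − 1/w)^N
- expected number passing one given cut-off birthday in 6 months = 0.5 N / w; chance of at least one = 1 − (1 − 0.5/w)^N

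| Assumed ages | w | Expected aged 17 (N = 20; 25) | Chance of at least one | Expected to pass cut-off (N = 20; 25) | Chance of at least one |
|---|---|---|---|---|---|
| 12-65 | 54 | 0.37; 0.46 | 31%; 37% | 0.19; 0.23 | 17%; 21% |
| 12-40 | 29 | 0.69; 0.86 | 50%; 58% | 0.34; 0.43 | 29%; 35% |
| 12-25 | 14 | 1.43; 1.79 | 77%; 84% | 0.71; 0.89 | 52%; 60% |

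The two groups overlap: under the protocol's cut at 18, anyone who crosses within 6 months is already 17 at baseline. A plausible count is 0 to 2 participants, that is 0% to 2/20 = 10%; a single case among 25 is 1/25 = 4%.

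**The case against.** The SAP scores by form, with separate recoding and totals for each, and SAP 1.1 ties the form to age. The age split may therefore be meant as a stand-in for the form completed. The table shells are in a separate document, so the final layout cannot be seen. The SAP split also agrees with the range printed on the short form: if sites go by that range, 17-year-olds complete the adult form, sit in the older stratum, and nothing mixes. The outlying text may then be the sentence in Protocol 8.2.2.

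This stands as a reason not to assume that mixing will occur, and as a reason to reconcile the protocol as well as the SAP. It does not remove the contradiction, because the protocol's rule is explicit and the SAP declares no departure from it.

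Three stronger readings are tempting and not supported:

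- A reader might infer that some change scores do compare different questionnaires. That needs a participant to pass the cut-off and the site to change the form; neither is documented.
- A reader might infer from the SAP's label that 16-year-olds have no form. The 12-16 stratum, the printed form and Protocol 8.2.2 all cover them, so the label is a slip.
- A reader might take 4-10% as a share of all PRO data. It is a share of participants on one of five instruments. The documents give no age-specific version of EQ-5D-5L, TSQM, WPAI or PGI-C.

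**Conclusion.** The point holds in a limited form. The age rules contradict each other at 17, and following both as written groups a short-form score with adult-form scores for a listed secondary endpoint. A change score across two forms is possible, because the reference date for age and the form at Month 6 are both left open.

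The likely extent is 0 to 2 of 20-25 participants on the haemophilia-specific questionnaire, which rests on assumed age ranges and may be zero. The analysis is descriptive and the primary endpoint is untouched. This is a minor point, worth correcting because the correction is nearly free.

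**What to change.** In SAP 4.3.2.1, tabulate by questionnaire completed (Haem-A-QoL or Haemo-QoL short form) in place of age, compute change from baseline only where both visits used the same form, and correct the short form's age label. This needs no new data and works even if collection has finished.

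In Protocol 8.2.2, reconcile the age cut with the printed form and the SAP, and state the date at which age is taken. For participants still to be assessed, keep the baseline form at Month 6. This part changes conduct and needs IRB approval under Protocol 11.1.1. It may also come late: Amendment 3 projected its enrolment figure to the end of 2023, and SAP version 3 is dated 9 January 2024.

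The cost in data is at most one or two change scores set to missing where the forms already differ.
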